4.5 Performance Analysis

All primary and secondary performance parameters will be analyzed using descriptive methods. For proportions two-sided exact 95% Clopper-Pearson confidence intervals will be calculated where appropriate.

4.5.1 Analysis of Primary Performance Variable

The primary performance parameter for this study is the percent of PICCs that remain in place through the required therapy time period (completion of therapy) (success/failure). A success will be defined as follows:

- subjects which still have the study peripherally inserted central line catheter in place
- subjects who did not have the study peripherally inserted central line catheter in place with the reason for peripherally inserted central line catheter removal:
 - “therapy completed / end of useful medical use (catheter stayed in place through the required therapy time)” or
 - “therapy changed or cancelled”.

The percentage of PICCs that remain in place through the completion of therapy (success) will be calculated by dividing successful cases by the total number of devices with non-missing data on success/failure in the evaluable set and displayed using frequency tables. 95% confidence interval will be calculated.

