## 1.2 Schedule of Activities

Procedure / Study Phase	Screening/ Enrollment	Insertion	Use and Maintenance	Removal / Last Study Visit* (End of Study)	Notes
Inclusion and exclusion criteria	X				
Informed Consent	X				
Baseline and demography	X				
Medical history	X				
Catheter insertion		X			
Ease of insertion survey		X			
Use and maintenance assessment			X		
Removal assessment				X	
AE monitoring		X	X	X	
Device deficiency monitoring		X	X	X	

\*Participants will be followed through device removal or  $180 \pm 14$  days post-insertion, whichever comes first.

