## **7.4 Use and Maintenance Procedures**

The PowerPICC device will be used for therapy as medically required, according to the IFU and hospital protocol. The device will be maintained (i.e., flushing, fluid locking, cleansing) and the site maintained (i.e., cleansing, dressing) according to the device specific IFU, standard medical practice, and hospital protocols.

When the participant is treated in an acute-care setting, the catheter/site will be assessed daily until the device is removed or until they are discharged with the device in place (then treated as an outpatient). When the participant is treated in an outpatient setting, the catheter/site will be assessed at each therapy visit until the device is removed, or until 180 days post-insertion ( $\pm 14$  days), whichever comes first. For the purposes of endpoint calculations, PICCs remaining in place after 180 days will be considered to have completed therapy.

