### 7.5.1 Device Removal Data

At the time of device removal, the following data will be collected:

- Date and time of device removal
- Reason for removal (e.g., completion of therapy, device failure)
- Site condition

Note: Should the catheter remain in place through 180 days without removal, day 180, or the last study visit occurring  $180 \pm 14$  days, will be documented as the final catheter day for the purposes of dwell-time calculations.

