## 8 PARTICIPANT DISCONTINUATION/WITHDRAWAL

### 8.1 Discontinuation/Withdrawal

- A participant may withdraw from the study at any time at his/her own request or may be withdrawn at any time at the discretion of the investigator or sponsor for safety, behavioral, compliance, or administrative reasons. This is expected to be uncommon.
- At the time of discontinuing from the study, no further data will be collected for the participant.
- If the participant withdraws consent for disclosure of future information, the sponsor may retain and continue to use any data collected before such a withdrawal of consent.
- Participants who withdraw or discontinue the study early (e.g., prior to PICC insertion) may be replaced.

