### 10.4.2 Performance

The percentage of PICCs that remain in place through the completion of therapy (success) will be calculated by dividing successful cases by the total number of cases (total number of participants completing therapy with single PICC / total number of participants); 95% confidence interval will be calculated.

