The PowerPICC device will be used for therapy as medically required, according to the Instructions for Use (IFU) and hospital protocol. The device will be maintained (i.e., flushing, fluid locking, cleansing) and the site maintained (i.e., cleansing, dressing) according to the device specific IFU, standard medical practice, and hospital protocols. When the participant is treated in an acute-care setting, the catheter/site will be assessed daily until the device is removed or until they are discharged with the device in place (then treated as an outparticipant). When the participant is treated in an outparticipant setting, the catheter/site will be assessed at each therapy visit until the device is removed, or until 180 days post-insertion (± 14 days), whichever comes first. For the purposes of endpoint calculations, peripherally inserted central catheters (PICCs) remaining in place after 180 days will be considered to have completed therapy.

Device Removal Procedure

The study device will be discontinued/removed when it is deemed medically appropriate by the participant's treating clinician (e.g., no longer needed, no longer functioning). Removal of the device will be performed according to the device specific IFU, standard medical practice, and hospital protocols.

Investigational Sites

Up to 20 sites in the EU will participate in this study. No more than 20% of participants may be enrolled at any one site.

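### SAP 4.5.1 counts a line still in place as success without the day-180 condition, so lines in situ at an early exit can raise the primary performance rate

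*SAP*

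**What the plan says.** **Success definition.** SAP 4.5.1 names three kinds of success. The first is "subjects which still have the study peripherally inserted central line catheter in place". The others are removal because therapy was completed and removal for "therapy changed or cancelled". The denominator is devices in the evaluable set with a non-missing success/failure value.

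**Day-180 rule.** Protocol 7.4 says, for endpoint calculations, that "PICCs remaining in place after 180 days will be considered to have completed therapy". SAP 1.1 repeats it: "peripherally inserted central catheters (PICCs) remaining in place after 180 days will be considered to have completed therapy". SAP 4.5.1 neither restates nor cites the rule.

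**Protocol formula.** Protocol 10.4.2 gives "total number of participants completing therapy with single PICC / total number of participants". It names no analysis population and does not mention changed or cancelled therapy.

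**Early exit.** Protocol 8.1 says: "At the time of discontinuing from the study, no further data will be collected for the participant". It expects withdrawal to be uncommon. SAP Table 1.2.1 has rows for withdrawal, loss to follow-up and death, but nothing links them to success or failure.

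**Where the in-place status is recorded.** It appears in SAP Appendix A under Removal (Table 3.5, Listing 3.6). The protocol schedule puts the removal assessment in the column "Removal / Last Study Visit* (End of Study)".

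**Declared changes.** SAP section 5 lists one change: the non-missing denominator.

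**Interim.** SAP 4.8 performs it at 50% enrolled. SAP 1.3 and protocol 10.6 target 50% completed, or sooner if reporting requires. Table 5.1.1, the primary performance table, is marked for the interim.

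**The concern.** SAP 4.5.1 is the text a programmer will code from, and it lacks the time condition set elsewhere for the same endpoint. A catheter in place on day 20, when the participant withdraws, has not been shown to last through the required therapy, yet the literal wording scores it as success. If no removal record was made, the line drops out as missing instead. Neither treatment is chosen in advance.

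This is one of two primary endpoints, reported for each device without a comparator, so the definition largely determines the reported rate. No planned summary table isolates the affected lines: Table 3.5 shows in-place status only as missing, no or yes on the evaluable set, and Table 1.2.1 shows exit status on the safety set.

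The reason "therapy changed or cancelled" raises a smaller question. The SAP lists it apart from completed therapy and counts it as success, but does not declare it as a choice beyond the protocol formula.

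**Working it through.** **The plan's own figures.** None is given for the performance endpoint. The sample-size section gives a half-width of 4.8 points for a 10% thrombosis rate at n = 150: 1.96 × √(0.10 × 0.90 / 150) = 4.80 points. It reproduces and is not in dispute. It supplies n = 150 per device and 450 in total, used below as the planned size; the evaluable set may be smaller.

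**The rules side by side, for a line in place at the last observation.**

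| Situation | SAP 4.5.1, literal | Protocol 7.4 / SAP 1.1 | If no removal record exists |
|---|---|---|---|
| Day-180 (± 14) assessment reached | success | completed therapy | not applicable |
| Withdrawal, loss or death before then | success | not covered | missing, outside denominator |

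The first row agrees. Protocol 7.5.1 supports using the visit window: its note begins "Should the catheter remain in place through 180 days without removal, day 180, or the last study visit occurring" and takes that day as the final catheter day. Only the second row is open.

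**Direction and size.** Let n be evaluable participants, S completers, e early exits in situ, p = S/n and f = e/n.
- Kept as not success: S/n.
- Missing: S/(n − e). The excess over S/n is p·f/(1 − f), which is never negative.
- Success: (S + e)/n. The excess over S/n is e/n, also never negative.

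One participant recoded as success adds 1/150 = 0.67 point to a device rate and 1/450 = 0.22 point to the total. With f = 1%, coding as success adds 1.0 point; coding as missing adds 0.61 point at p = 60% and 0.91 point at p = 90%.

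**Illustrations (S and e are assumed; the documents give no counts).**

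| n = 150 | Not success | Missing | Success |
|---|---|---|---|
| S = 135, e = 3 | 135/150 = 90.0% | 135/147 = 91.8% | 138/150 = 92.0% |
| S = 114, e = 8 | 114/150 = 76.0% | 114/142 = 80.3% | 122/150 = 81.3% |

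**Benchmark against sampling error.** Exact 95% Clopper-Pearson half-widths at n = 150 are 8.1 points at 90/150 (60.0%), 7.2 at 112/150 (74.7%) and 5.1 at 135/150 (90.0%). The smallest number recoded as success that shifts the rate by that much is 13 (13/150 = 8.7%), 11 (7.3%) and 8 (5.3%).

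**Changed or cancelled therapy.** The same e/n arithmetic applies if such removals are not regarded as completions: with 114 other successes, 8 such removals give 122/150 = 81.3% counted and 114/150 = 76.0% not counted.

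**Interim.** Assume uniform accrual over A days. At 50% enrolled, the share of those enrolled who could have reached day d is max(0, A/2 − d)/(A/2). With the protocol's 6 to 12 months (A = 182.5 to 365), this is 0 to 1.4% for d = 180 and 0 to 9.0% for d = 166. It is not the share who have completed, because removal also completes a participant. It shows only that nearly all lines still in place at that point would be short of day 180.

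**The case against.** The strongest reply is that the day-180 rule is in the SAP: section 1.1 states it for endpoint calculations, so it can be read into 4.5.1. In-place status is a removal or last-visit item, so for most participants it is recorded only at removal or day 180. The case report form is not available, and the removal reasons in Table 3.5 are abbreviated. If death or withdrawal is coded as a removal reason, 4.5.1 already makes it a failure. If no record exists, the line is missing, and that path is planned: no imputation, review of missing endpoint data (SAP 4.7), and a declared non-missing denominator.

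Much of this stands. A reader might infer that the plan intends to score early dropouts as successes, or that the rate is materially inflated. The documents show neither; they show a literal wording that permits it. But reading SAP 1.1 into 4.5.1 only bars success before day 180 and does not choose between failure and missing. The review of missing data does not override a rule that yields a non-missing success.

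A reader might also call the changed-or-cancelled rule an error. The documents do not support that: if therapy is cancelled, the line was no longer required and has not failed, and the protocol leaves technical detail to the SAP. Table 3.5 and Listing 3.6 (an interim listing that carries device success) make the coding auditable. The point is only that section 5 does not declare it.

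Nor can the interim timing be called a clear breach, since the protocol allows an earlier look and 50% enrolled cannot come after 50% completed.

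Finally, the Table 3.5 shell contains counts for skin condition at removal, with 180 of 319 missing. Their cause is not stated, so they are no estimate of early exits in situ.

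**Conclusion.** The point holds as a gap in the operative definition of a primary endpoint. It is confined to lines in situ at withdrawal, loss to follow-up or death before the day-180 window. For these, literal coding as success or exclusion as missing gives a rate equal to or above completers over all evaluable participants.

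The size cannot be known from the documents: it is 0.67 point per participant recoded as success at n = 150, and it would take 8 to 13 such participants per device to match one exact half-width at assumed rates of 90% to 60%. Withdrawal is expected to be uncommon, and there is no test or stopping decision. It is worth fixing because the rule is a primary definition and the correction is cheap, not because a large bias has been shown. Confidence is medium, since the case report form route for early exits is unseen. The changed-or-cancelled and interim matters are points of documentation.

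**What to change.** 1. In SAP 4.5.1, count an in-place line as success only when the Table 1.2.1 completion status is completed, meaning that the 180 ± 14-day last assessment was reached. Never count a line in situ at an earlier exit as success. A bare day count will not do: a cut-off of at least 166 days would score a withdrawal at day 170 as success, whereas completion status already separates it.
2. Show earlier exits in situ as a separate row in Table 5.1.1. Keep the declared non-missing rate, which excludes them, as primary. Add a sensitivity rate that keeps them in the evaluable-set denominator as not success. Label it a lower bound, since their outcome is unknown. Give exact confidence intervals for both.
3. Declare in SAP section 5 that "therapy changed or cancelled" counts as success, and report the rate with and without it.
4. Reconcile the interim trigger in SAP 4.8 with SAP 1.3 and protocol 10.6. State that lines ongoing at the interim cut-off are not successes and lie outside the interim denominator.

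The cost is SAP wording, one derived variable, an extra table row and additional rates. Completion status and removal reasons are already collected (Listings 1.2.1 and 3.6). The downside is slightly more programming and a possibly less favourable rate.

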### 4.3 End of Study Definition

A participant is considered to have completed the study if he/she has completed all phases of the study including study device removal or achievement of  $180 \pm 14$ -day dwell time (last study assessment). Data collection will cease for the study participant at this point regardless of whether or not the device remains in place.

The end of the study is defined as the date of the last study assessment of the last participant in the study.

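### SAP 4.5.1 leaves out the day-180 completion rule, so the primary performance endpoint depends on where the last visit falls between days 166 and 194

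*SAP*

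**What the plan says.** The day-180 rule appears three times. Protocol 7.4 states it in full: "For the purposes of endpoint calculations, PICCs remaining in place after 180 days will be considered to have completed therapy". The Protocol 1.1 synopsis and SAP 1.1 carry the same rule.

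Follow-up outside hospital continues until removal or "until 180 days post-insertion (± 14 days), whichever comes first", that is, to a last visit between day 166 and day 194. Protocol 4.3 closes the record at removal or at that last assessment: "Data collection will cease for the study participant at this point regardless of whether or not the device remains in place".

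SAP 4.5.1 defines success for the primary performance variable by two criteria:

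- "subjects which still have the study peripherally inserted central line catheter in place"; or
- "subjects who did not have the study peripherally inserted central line catheter in place with the reason for peripherally inserted central line catheter removal" being either that therapy was completed or "therapy changed or cancelled".

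Neither criterion mentions a day, uses the removal date or refers back to SAP 1.1. The only departure declared under SAP 5 (Changes from Protocol) is the restriction of denominators to non-missing data.

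**The concern.** One primary endpoint has two rules, and they can disagree on the same line. SAP 4.5.1 gives a complete success list for a variable labelled success/failure. A line removed for occlusion or thrombosis is therefore not a success on any day, including days on which the day-180 rule says therapy was already complete. In the other direction, a line in place at an early last visit is a success although it has not passed day 180.

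The result for a participant can then turn on when a routine visit was booked within a 28-day window (194 − 166 = 28). Two programmers working from different sections of the SAP could report different completion rates from the same data.

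**Working it through.** **Classification.** Day of removal, reason and last visit are set; each rule is then applied as written.

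| Line | Day-180 rule | SAP 4.5.1 |
|---|---|---|
| A. Last visit day 182, in place; fails day 186, after observation ends | completed | success |
| B. Removed for occlusion day 186; last visit was due day 190 | completed | not a success |
| C. Removed for occlusion day 178; last visit not yet held | not reached | not a success |
| D. Last visit day 167, in place; fails day 178, after observation ends | not determined | success |

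A and B are the same line with different visit dates, as are C and D. SAP 4.5.1 scores each pair differently.

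**The plan's own figures.** The documents give no expected completion rate, no share of lines reaching day 180 and no failure rate. The only precision figure is for thrombosis: 1.96 × √(0.10 × 0.90 / 150) = 4.8 points, as stated in Protocol 10.2 and SAP 1.2. It serves here only as a yardstick.

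**Assumptions for size (not from the documents).** Share of lines reaching day 180: p = 10% to 50%. Failure removals: h = 1 to 3 per 1000 catheter-days. Planned n = 150 per device type (SAP 1.2).

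**Lines removed for failure after day 180 (pattern B).** The affected share is p × (1 − exp(−h × d)), where d is the number of days observed past day 180.

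- Every last visit on day 194 (d = 14): from 0.10 × (1 − e^(−0.014)) = 0.14 points to 0.50 × (1 − e^(−0.042)) = 2.06 points. On 150 lines this is 0.2 to 3.1.
- Last visits spread evenly over days 166 to 194: half fall after day 180, on average 7 days past it, so mean d = 0.5 × 7 = 3.5. To first order the share runs from 0.10 × 0.001 × 3.5 = 0.035 points to 0.50 × 0.003 × 3.5 = 0.525 points. On 150 lines this is 0.05 to 0.8.

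Wider inputs (10 to 60 lines per device type at day 180, 0.5 to 5 failures per 1000 days) give 0.07 to 4.1 lines with every last visit on day 194, and 0.02 to 1.1 with even spread.

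**Lines credited early (pattern D).** Against a horizon fixed at day 180, the error is the share of these lines that would fail between the last visit and day 180. With even spread, the mean shortfall is again 0.5 × 7 = 3.5 days, so the same first-order formula gives about 0.04 to 0.5 points, upward. The two errors roughly cancel under even spread. With every last visit on day 194 only the downward error exists; with every last visit on day 166, only the upward one.

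**Effect per line.** One reclassified line moves a device-type rate by 1/150 = 0.67 points and the total by 1/450 = 0.22 points. For an assumed 120/150 (80.0%, exact 95% CI 72.7 to 86.1), reclassifying three lines gives 123/150 (82.0%, 74.9 to 87.8).

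**The case against.** The strongest defence is that SAP 1.1 already contains the rule, expressly for endpoint calculations. SAP 4.5.1 defines neither failure nor the date at which in-place status is judged, so the two sections can be read together. That much stands: a careful programmer might apply the rule. But 4.5.1 is the operative definition and its list is closed, so the scoring should not depend on the programmer supplying a term from another section.

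A second defence is that the ± 14-day window is itself the end point. Protocol 4.3 accepts a dwell of 180 ± 14 days as completion, and Protocol 7.5.1 accepts day 180 or the last visit as the final catheter day. On that reading the day-180 rule is a convention for lines in place when observation ends. This is a fair account of lines last seen on days 166 to 179, and a good reason to keep counting them as successes. It does not settle a line removed on day 186, which was in place after 180 days on the plain words. Protocol 7.5.1 is limited to dwell-time calculations.

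Third, all analyses are descriptive, and Listings 3.1 and 3.6 show the insertion date, removal date, reason and success status for each participant, so affected cases can be found. This limits the weight of the point.

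A reader might infer that SAP 4.5.1 biases the completion rate downward. The documents do not support that: early crediting on days 166 to 179 works upward, and visit timing is not given. A reader might also infer that the SAP dropped the day-180 rule without declaring it. SAP 1.1 restates the rule, so an omission in 4.5.1 is the more natural reading.

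**Conclusion.** The inconsistency is real and concerns a primary endpoint. As written, SAP 4.5.1 does not apply the rule that PICCs "remaining in place after 180 days will be considered to have completed therapy", and classification near day 180 depends on visit timing.

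The effect is small. It is probably under one participant per 150 in each direction if last visits are evenly spread, and at most about 3 of 150, downward, if every last visit fell on day 194. Both figures rest on the assumed 10–50% of lines reaching day 180 and 1–3 failure removals per 1000 catheter-days. The net direction is not determined by the documents. No hypothesis test depends on it. The point is limited to participants followed to removal or to a completing last visit; lines in place at an early withdrawal are a separate question. It is a low-priority correction, worth making because it costs almost nothing.

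**What to change.** In SAP 4.5.1:

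1. Derive dwell as removal date minus insertion date, or last-visit date minus insertion date if the line is still in place.
2. Apply the SAP 1.1 rule explicitly: a line in place beyond day 180 is a success whatever happens later. A removal on or before day 180 is judged by the reasons already listed.
3. State that lines still in place at a completing last visit on days 166 to 179 count as successes by convention. Say also how a line seen in place on day 180 itself is counted.
4. In a footnote to Table 5.1.1, give the number removed for failure after day 180 and the number last seen in place on days 166 to 179. Add the completion rate recalculated without the second group as a sensitivity figure.

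That sensitivity figure removes only successes, so it will be lower than the main rate unless the group is empty or every line is a success. For example, taking 7 such lines out of 120/150 gives 113/143 = 79.0%. It shows how much rests on the convention and is not a corrected estimate.

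Adding only a success criterion for removals after day 180 would not be enough: it would leave the early-visit side unstated and the dependence on visit timing half in place.

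The cost is a few lines of SAP text, one date condition and a footnote. Insertion date is in Listing 3.1, removal date and reason in Listing 3.6, and study completion date in Listing 1.2.1. No new data are needed.
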